#### 8.2. Statistical Methods

Optimal quantification will be the simplest model that shows strong correlations between acetate binding and amyloid SUVR. C-Acetate binding and amyloid SUVR will be analyzed using PMOD for modeling and static uptake estimates and Statistical Parametric Mapping using T1 MRI for coregistration and template-based regional segmentation. We will compare and correlate amyloid and acetate quantification using both Pearson's correlation and non-parametric Spearman's correlation.

The expected positive correlation between acetate binding and CSF cytokine levels will be evaluated. Global, regional and voxel based correlations will be performed between acetate uptake and amyloid PET SUVR from MCI subjects and cognitively normal subjects with a positive Amyloid scan. Acetate binding in voxels with amyloid SUVR below, between 100-125%, or above 125% of previously validated thresholds will also be compared.

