
	4. A brain MRI is required. If a brain MRI has been performed within 6 months of enrollment to this study and of adequate quality that scan may be used for the study analysis, subjects who do not have a brain MRI will undergo a brain MRI as a part of this study			
	
 
Participants must be informed of the investigational nature of this study and provide written informed consent in accordance with institutional and federal guidelines prior to study-specific procedures.
 
			
	Exclusion Criteria (for both cohorts)			
	Inability to tolerate or contraindication to imaging procedures (PET/CT or MRI) in the opinion of an investigator or treating physician			
	
 
History of stroke or other neurological disease that in the opinion of the investigator might interfere with evaluation of the C-Acetate scan
 
			
	
 
Any medical or psychological conditions that, in the opinion of the investigator, would compromise the subject's safety or successful participation in the study.
 
			
Study Product	[  C]Acetate			
Statistical Methodology	Several methods for acetate binding quantification will be tested and compared; optimal quantification will be the simplest model that shows strong correlations between acetate binding and amyloid SUVR.  C-Acetate binding and amyloid SUVR will be analyzed using PMOD for modeling and static uptake estimates and Statistical Parametric Mapping using T1 MRI for co-registration and template-based regional segmentation. We will compare and correlate amyloid and acetate quantification using both Pearson's correlation and non-parametric Spearman's correlation.			
	The expected positive correlation between acetate binding and CSF cytokine levels will be evaluated. Global, regional and voxel based correlations will be performed between acetate uptake and amyloid PET SUVR from MCI subjects. Acetate binding in voxels with amyloid SUVR below, between 100-125%, or above 125% of previously validated thresholds  will also be compared.			

This document is a protocol for a human research study. This study is to be conducted according to US and international standards of Good Clinical Practice (FDA Title 21 part 312 and International Conference on Harmonization guidelines), applicable government regulations and Institutional research policies and procedures.

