Our proposed study aims to use C-acetate PET/CT to preliminarily test and validate methods for imaging astrocyte activation as an early indicator of neuroinflammation in AD. C-Acetate PET/CT has been shown to quantify astrocyte activation *in vivo*, but no reports have evaluated its potential in AD. We propose to test C-Acetate PET/CT as a marker for astrocyte activation associated with pathologic amyloid deposition in AD. We will compare binding between subjects with early stage AD and cognitively normal subjects with positive Amyloid PET and healthy controls. Further, we will investigate the correlation between amyloid and acetate binding. If we find increased astrocyte activation in response to cerebral amyloid by showing a group difference in brain acetate uptake between disease and controls or a strong correlation between acetate and amyloid PET/CT binding. Validating neuroinflammation markers in AD ultimately may

guide therapeutic modulation of beneficial and damaging neuroinflammation to slow disease progression, as well as providing new insights into AD pathophysiology.

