# 2.2. Secondary Objectives

- Correlate C-acetate uptake to areas of greater amyloid plaque burden quantified on Amyloid PET/CT
- Compare C-acetate in areas of mildly elevated PET SUVR to areas with high or sub-threshold amyloid burden
- Correlate C-acetate uptake to levels of inflammatory markers in CSF

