Venous Blood Sampling: Venous blood samples will be collected at approximately 2, 5, 10, 20, 40 and 60 minutes post-injection to measure radioactive counts in the blood. The actual time of each blood draw will be recorded. Sampling may be reduced to fewer time points if experience from the first subjects indicates fewer time points will be sufficient for analysis. The total amount of blood drawn for venous sampling will be approximately 12 mL (about 3 teaspoons). If a second IV line is not able to be successfully accessed or an investigator does not think the patient can tolerate a second IV for blood draws this may be omitted at the discretion of an investigator, this will be recorded in the CRF and will not be considered a protocol deviation.

Adverse events that are grade 3 or higher will be recorded for the period up to 10 hours post injection of the radiotracer. Research personnel will conduct follow up by telephone

or in person, depending on the subject's schedule. Follow up should take place the next available business day (i.e. not a weekend or a holiday).

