# 7. Image Interpretation

# 7.1. C-acetate PET/CT Image Analysis

The low dose CT from the C-Acetate PET/CT scans will be reviewed by a trained radiology reader designated by the principal investigator. Any findings that may affect the clinical course of the subject will be reported to the patient's physician. The C-Acetate PET/CT data is not validated for clinical use; as such, results will not be reported.

C-Acetate PET/CT, Amyloid PET/CT and MRI images will be coregistered to allow template-based determination of regions of interest (ROI) on PET. We will obtain venous blood samples to calibrate an image-based arterial input function for the kinetic analysis.

Standardized uptake value ratio (SUVr), the ratio of regional to reference uptake, will be calculated with cerebellum as reference for both the C-Acetate and the amyloid PET/CT images. To account for atrophy, partial volume correction will be applied. Regional quantification will be performed using analysis software, such as Scenium (Siemens Medical Systems), PMOD (PMOD Technologies), or SPM (Wellcome Trust). Voxel based comparisons of PET/CT and MRI data may also be performed. We may also use graphical (Patlak) analysis, and with kinetic analysis using a two compartment model, which we have tested on other applications such as brain tumors   . Plasma CO2 will be estimated from venous samples, which will each be divided into two aliquots, one into acidic and the other into basic solution. Radioactivity in each aliquot will be counted with the difference in counts between acidic and basic used to calculate plasma CO2, which will be used in kinetic analysis of acetate binding.

Optimal quantification of acetate binding will be the simplest model that shows strong correlations between acetate binding and amyloid SUVR. Acetate binding and amyloid SUVR will be analyzed using PMOD for modeling and static uptake estimates and Statistical Parametric Mapping using T1 MRI for coregistration and template-based regional segmentation. We will compare and correlate amyloid and acetate quantification using both Pearson's correlation and non-parametric Spearman's correlation.

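### The optimal acetate model is chosen for correlating strongly with amyloid SUVR, and that same correlation is the first secondary objective, so it is not independent evidence

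*Combined protocol and SAP*

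**What the plan says.** The Study Summary (Statistical Methodology) announces a comparison of methods: "Several methods for acetate binding quantification will be tested and compared". Section 8.2 gives the rule for choosing among them: "Optimal quantification will be the simplest model that shows strong correlations between acetate binding and amyloid SUVR". Section 7.1 has the same rule.

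Section 7.1 commits to a static SUVr with cerebellar reference and adds optional candidates: "We may also use graphical (Patlak) analysis, and with kinetic analysis using a two compartment model".

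The first secondary objective (section 2.2) is to correlate acetate "uptake to areas of greater amyloid plaque burden quantified on Amyloid PET/CT". Section 8.2 carries this out with global, regional and voxel-based correlations in the MCI subjects and the cognitively normal amyloid-positive subjects; the Study Summary names the MCI subjects only. Both Pearson and Spearman coefficients are planned. Section 1.2 names two findings that would show increased astrocyte activation in response to amyloid: a group difference in uptake, "or a strong correlation between acetate and amyloid PET/CT binding".

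Section 7.2 lists regional acetate SUVR among the primary analysis variables.

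**The concern.** The quantity that decides which model is optimal is the quantity that the first secondary objective sets out to estimate. A model can earn the label only by showing a strong correlation with amyloid SUVR. Once it has, its strong correlation is no longer a finding that could have gone the other way.

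The plan has none of the usual protections. It describes no separate development sample and no cross-validation. It gives no numerical meaning for strong, no closed list of candidates in order of simplicity, and no selection criterion unrelated to amyloid. Listing SUVR in section 7.2 does not close the gap, because no sentence says that the amyloid correlation will be reported for SUVR whatever the model comparison shows.

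At stake is the reading in section 1.2 of a strong correlation as evidence of astrocyte activation. Section 8.1 adds that this pilot will inform the sample size of a larger study, so an overstated correlation could carry forward into that planning.

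**Working it through.** **The plan's own figure.** There is none to reproduce. The documents give no target correlation, alpha, power or cut-off for this analysis.

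**Inputs from the documents.** Section 3 gives 14 MCI subjects and 5 cognitively normal amyloid-positive subjects. The correlation therefore rests on at most 14 + 5 = 19 subjects under section 8.2, or 14 under the Study Summary. Section 7.1 names three candidates: static SUVr, Patlak and a two-compartment model.

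**Assumptions not in the documents.** The three candidates are exchangeable, with pairwise correlation 0.9 or 0.7. They are taken in a fixed order of simplicity, and the first with r at or above the cut-off is reported; if none reaches it, the simplest is reported. One global between-subject Pearson r is computed per candidate. A positive result means passing a one-sided 5% test. Each setting was simulated 200,000 times.

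**Critical values.** With r = t / √(t² + n − 2):
- n = 19: t(0.95; 17) = 1.740, so r = 1.740 / √(3.03 + 17) = 0.389.
- n = 14: t(0.95; 12) = 1.782, so r = 1.782 / √(3.18 + 12) = 0.458 (before rounding, 0.4575).

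**No true association: chance that the reported model passes the one-sided 5% test** (pairwise correlation 0.9 / 0.7; one fixed measure gives 5.0%)

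| Meaning of strong | n = 19 | n = 14 |
|---|---|---|
| p < 0.05 | 8.2% / 10.5% | 8.2% / 10.6% |
| r ≥ 0.4 | 7.7% / 9.9% | 6.8% / 9.4% |
| r ≥ 0.5 | 5.4% / 6.3% | 6.7% / 8.7% |
| r ≥ 0.6 | 5.1% / 5.2% | 5.3% / 6.1% |

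**No true association: chance that at least one candidate reaches r ≥ 0.5.** At n = 19 it is 2.7% / 3.4%, against 1.5% for one measure. At n = 14 it is 5.8% / 7.6%, against 3.4%.

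**Number of candidates** (n = 19, cut-off p < 0.05). Two candidates give 6.9% / 8.2%; four give 9.0% / 12.3%.

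**True r = 0.3, n = 19: mean reported r over all trials**

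| Meaning of strong | Mean r (0.9 / 0.7) | Excess over fixed measure (0.293) |
|---|---|---|
| p < 0.05 | 0.307 / 0.334 | 0.014 / 0.041 |
| r ≥ 0.5 | 0.302 / 0.321 | 0.009 / 0.028 |
| r ≥ 0.6 | 0.297 / 0.307 | 0.004 / 0.014 |

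The bias is therefore about 0.00 to 0.04. If only the trials that pass at p < 0.05 are counted, the mean r is about 0.50. One fixed measure treated the same way gives about 0.52, so that figure reflects conditioning on success and not the selection rule.

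**Primary comparison, 14 MCI against 6 controls.** When selection uses only the 19 amyloid-positive subjects, the one-sided 5% t-test has an error rate of 5.0% to 5.1% (60,000 replicates). If controls who happen to have amyloid scans also entered the selection, it would be about 6%.

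The regional and voxel-based correlations were not simulated.

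**The case against.** The best case for the plan is that it already leans on SUVR. Section 7.2 lists acetate SUVR and no kinetic parameter, and section 7.1 makes the kinetic analyses optional. The rule takes the simplest adequate model, not the one with the highest correlation, and static SUVR is plausibly the simplest. On that reading a kinetic model replaces SUVR only when SUVR is not strong. With no true association this happens in 0.3% to 2.0% of trials (n = 19, cut-off 0.5 or 0.6), 0.9% to 4.1% (n = 14, same cut-offs), and at most about 5.5% when strong means p < 0.05. This is also a pilot, and comparing quantification methods is part of its purpose. The sentence in section 1.2 is an unfinished conditional and does not claim independent evidence.

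Much of this stands as a limit on size, and the figures above already include the effect of choosing the simplest model. The simulated error rates also belong to a one-sided 5% test that the plan does not specify, and to a global correlation, whereas the objective is worded in terms of areas of the brain.

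It does not remove the overlap. No sentence ties the amyloid correlation to SUVR regardless of the model comparison, and three places in the document define the optimal measure by that correlation. Pilot status lowers the stakes without making the result independent. Agreement with amyloid can be a reasonable criterion for choosing a measure, but the same agreement cannot then test whether acetate tracks amyloid.

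A further fair point is that regional SUVR is not a single number, since the plan names neither a target region nor a static time window for acetate. Fixing SUVR alone would leave that choice open.

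**Conclusion.** The concern holds and should be fixed. The circularity follows from the text and does not depend on any simulated figure: the selection rule and the first secondary objective use the same two quantities, apparently in the same subjects, with no held-out data.

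The numerical consequence is modest. Under the stated assumptions the false-positive rate is about 5% to 11% instead of 5%, with the upper end only if strong means p < 0.05, and the bias in r is at most about 0.04 at n = 19 and true r = 0.3. Confidence is high for the overlap in the text. The size is illustrative, because the plan gives no cut-off, alpha or between-method correlation. The primary comparison is not materially affected if selection is confined to amyloid-positive subjects, as section 8.2 implies.

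**What to change.** In the Study Summary and sections 7.1 and 8.2:

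- State that regional acetate SUVR with cerebellar reference, already a primary analysis variable in section 7.2, is the fixed measure for the main acetate-amyloid correlation and for the primary comparison. Naming the region or composite and the static time window in the same sentence would make it a single measure.
- Name one correlation coefficient in advance and report its value whatever its size.
- Report the amyloid correlations for every other quantification tried, and label any choice of an optimal model based on them as exploratory.

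SUVR has a practical advantage. Section 6.2 says of the venous sampling that "this may be omitted at the discretion of an investigator", so kinetic estimates may exist for fewer subjects. Where blood data exist, kinetic models could optionally be compared on goodness of fit and parameter precision, which do not involve amyloid.

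The cost is one or two sentences in each place, with no new data or visits. The small downside is that SUVR may not be the most sensitive measure of acetate uptake.

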### 8.3. Subject Population(s) for Analysis

The primary analysis population will consist of age matched cohorts of amnestic MCI patients and normal controls. Patients will be recruited from the clinical practices of Penn Memory Center, Frontotemporal Lobar Degeneration Center, or other clinics of the University of Pennsylvania Health System. All subjects with an C-acetate PET/CT will contribute to the primary analysis.

### 9. Adverse Events

#### 9.1. Definitions

Adverse Events are classified as serious or non-serious.

Adverse Events that do not meet the established criteria for Serious Adverse Events (see below) should be regarded as **non-serious adverse events**.

#### **Adverse Event**

An **adverse event** (AE) is any untoward medical occurrence in a participant that does not necessarily have a causal relationship with the study procedure. It is any symptom, sign, illness or experience that develops or worsens in severity during the course of the

study procedure. Intercurrent illnesses or injuries should be regarded as adverse events. Abnormal results of diagnostic procedures are considered to be adverse events if the abnormality:

- results in study withdrawal
- Is associated with a serious adverse event
- is associated with clinical signs or symptoms
- leads to additional treatment or to further diagnostic tests
- is considered by the investigator to be of clinical significance

#### **Serious Adverse Event**

A Serious Adverse Event (SAE) is any Adverse Event that is:

- fatal
- life-threatening
- requires or prolongs hospital stay
- results in persistent or significant disability or incapacity
- a congenital anomaly or birth defect
- an important medical event

## **Expected and Unexpected Adverse Events**

AEs may be **expected** or **unexpected**:

- An **expected AE** is one that is described in the protocol, the ICF, or the investigator's brochure.
- An unexpected AE is one that has not been described in the protocol, the ICF, or the investigator's brochure.

#### **Adverse Event Grading**

Grade denotes the severity of the AE.

- 1 Mild
- 2 Moderate
- 3 Severe
- 4 Life-threatening or disabling
- 5 Fatal

### **Adverse Event Attribution**

Attribution is used to determine whether an AE is related to a study treatment or procedure.

Attribution categories are:

**Definite:** The AE is **clearly related** to a treatment or procedure **Probable:** The AE is **likely related** to a treatment or procedure **Possible:** The AE **may be related** to a treatment or procedure **Unlikely:** The AE is **likely unrelated** to a treatment or procedure **Unrelated:** The AE is **clearly not related** to a treatment or procedure

### **Important Medical Events**

Important Medical Events are those events that may not be immediately life threatening, but are clearly of major clinical significance. They may jeopardize the subject's health and may require medical intervention.

# **Preexisting Condition**

A preexisting condition is a condition that is present at the start of the study. A preexisting condition should be recorded as an adverse event if the frequency, intensity, or the character of the condition worsens during the study period.

## **General Physical Examination Findings**

At screening, any clinically significant abnormality should be recorded as a preexisting condition. At the end of the study, any new clinically significant findings/abnormalities that meet the definition of an adverse event must also be recorded and documented as an adverse event.

# **Post-Study Adverse Event**

All unresolved adverse events should be followed by the investigator until the event is resolved or the subject is lost to follow-up.

### **Abnormal Laboratory Values**

A clinical laboratory abnormality should be documented as an adverse event if the Principal Investigator believes the abnormality is related to participation in the study.

## Hospitalization, Prolonged Hospitalization or Surgery

Any adverse event that results in hospitalization or prolonged hospitalization should be recorded as a serious adverse event. The event should be reported if the Principal Investigator believes the hospitalization is related to participation in the study.

# **Adverse Event Reporting Period**

The study period during which adverse events must be reported is normally defined as the period from the initiation of any study procedures to the end of the study treatment follow-up. For this study, the study treatment follow-up is defined as 10 hours following the administration of the study radiotracer, C-acetate.

### 9.2. Recording of Adverse Events

At each study visit session, the Principal Investigator or designee, must seek information from the subject in reference to any adverse events specific to imaging procedures or injection of C-acetate that may have occurred by specific questioning and as appropriate by examination. Information on all adverse events should be recorded in as much detail as possible on a source document or the medical record and entered on the Adverse Event Log.

All adverse events occurring during the AE reporting period of 10 hours post C-acetate injection will be recorded. The clinical course of each event should be followed until resolution, stabilization, or until it has been determined that the study treatment or participation is not the cause. Serious adverse events that are still ongoing at the end of the study period must be followed up to determine the final outcome. Any serious adverse event that occurs after the study period and is considered to be possibly related to the study imaging or study participation should be recorded and reported immediately.

The PI should be contacted immediately to determine the reporting requirements for the event as outlined in the protocol.

The clinical course of each event should be followed until resolution, stabilization or until it has been determined that the investigational agent or study procedure is not the cause of the event.

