# 4. Participant Selection

### 4.1. Inclusion Criteria for Cohort 1: Amnestic MCI

- **4.1.1.** Participants will be at least 55 years of age
- 4.1.2. An Amyloid brain PET/CT is required. If a Amyloid brain PET/CT has been performed within 6 months of enrollment to this study and of adequate quality that scan may be used for the study analysis, subjects who do not have a Amyloid brain PET/CT will undergo an Amyloid brain PET/CT as a part of this study
- 4.1.3. Mini-mental status examination (MMSE) score ≥ 24 at screening visit
- 4.1.4. A brain MRI is required. If a brain MRI has been performed within 6 months of C-Acetate PET/CT and of adequate quality that scan may be used for the study analysis, subjects who do not have a brain MRI will undergo a brain MRI as a part of this study
- 4.1.5. Participants must identify a study partner who is willing to accompany the patient to study visits
- 4.1.6. Participants must be informed of the investigational nature of this study and provide written informed consent in accordance with institutional and federal guidelines prior to study-specific procedures. If the patient is unable to provide informed consent, the patient's legal representative may consent on behalf of the patient but the patient will be asked to confirm assent.

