### 4.5. Subject Recruitment and Screening

For the amnestic MCI cohort, potential subjects, or their legally authorized representative (as appropriate), will be allowed to read a written informed consent form. The principal investigator or designee will explain all study procedures, risks, and alternative therapies. The subject and legally authorized representative will have an opportunity to have all questions answered by a physician. The subject will then sign and date the informed consent form, indicating willingness to participate in the study.

Subjects with neurodegenerative diseases are potentially a vulnerable population with compromised mental capacity. Investigators should take extra care to evaluate a patient's ability to give consent. If the subject is capable of giving informed consent then the subject should sign on the consent line of the informed consent form. The designated study partner should sign as well, indicating that they have witnessed the subject's consent, and further agree to participate as a study partner.

If the subject is not capable of giving consent, consent may be given by a legally authorized representative. However, it is expected that all subjects entering this study should at least have the capacity to understand that they are engaging in a research study and should affirm that they do not object to participating, by signing on the Subject Assent line of the consent form. If the legally authorized representative is also the designated study partner they should sign the study partner line of the consent form as well, indicating that they have witnessed the subject's assent, and further agree to participate as a study partner.

All informed consent forms must be approved by the appropriate Institutional Review Board (IRB). In some cases a verbal consent discussion will be carried out by phone prior to scheduling of Amyloid or C-Acetate PET/CT scans. Healthy volunteers will be contacted by phone to discuss the study. For candidates for the MCI cohort a verbal consent discussion by phone will only occur if both the patient and the study partner are available for the discussion. No study related procedures shall be performed prior to completion of the informed consent process, and signing of the consent form. A copy of the signed informed consent should be given to the patient and/or their legally authorized representative for their records.

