<sup>4 Optional: Patients who have previously had CSF stored or tested will not be asked to repeat these procedures. Timing of this will vary depending on if the patient has already had this done as part of clinical care or another study. If it is being performed prior to the imaging, lumbar puncture should occur a minimum of 48 hours prior to the C-Acetate PET/CT scan.

<sup>5 Neuropsychological test battery will include the following tests:

 Venous blood samples will be taken during the C-Acetate PET/CT imaging session in order to measure radioactive counts in the blood. If a second IV line is not able to be successfully accessed or an investigator does not think the patient can tolerate a second IV for blood draws this may be omitted.

 Follow up may occur by telephone or in person, depending on the subject's schedule. Follow up should take place the next available business day (i.e. not a weekend or a holiday). The AE monitoring period is 10 hours following C-acetate injection

 Screening assessments may be performed over multiple days

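### For the amnestic MCI cohort, the plan names only the subject as adverse event informant and gives the required study partner no role at the next-business-day contact, so transient events at home may be missed

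*Combined protocol and SAP*

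**What the plan says.** Section 9.2 sets the method for visits: at each session the investigator or designee "must seek information from the subject in reference to any adverse events" linked to imaging or the tracer injection, by specific questions and, where appropriate, examination. No other informant is named.

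The later contact is described elsewhere. A note to the study calendar in Section 6 says: "Follow up may occur by telephone or in person, depending on the subject's schedule". Section 6.2 says: "Research personnel will conduct follow up by telephone" or in person. Both place the contact on the next business day, with weekends and holidays excluded. Neither says who is to be spoken to.

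The reporting period in Section 9.1 ends 10 hours after injection. Section 6.2 describes a 60-minute scan that starts at about the time of injection, and Section 1.3 has trained personnel watch for allergic reaction during that procedure.

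For Cohort 1, Section 4.1 states: "Participants must identify a study partner who is willing to accompany the patient to study visits". The same section sets an MMSE of at least 24 and allows consent through a legal representative. Section 6.1 lets a designated decision maker report events after a lumbar puncture. There is no matching provision for the tracer injection.

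**The concern.** The cohort selected for impaired episodic memory provides most of the planned tracer injections. For most of the reporting window, an event enters the record only if someone remembers it at the next contact. The plan names the person least well placed to remember, and it does not use the partner whom it already requires.

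What is at stake is a complete safety record. Section 9.3 makes unexpected events reportable whatever their grade or attribution, so a mild, short-lived event at home matters to the sponsor. If nobody recalls it, the reporting steps never start.

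**Working it through.** The plan states no figure on this point, so there is none to reproduce. The check has three steps.

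**1. Share of the window under observation.** Inputs: a 10-hour window (Section 9.1) and a scan of about 60 minutes (Section 6.2).

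60 / (10 × 60) = 60 / 600 = 10%.

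About 9 of the 10 hours fall after the scan. I assume no planned observation after the scan, since none is described.

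**2. Delay to the follow-up contact.** Input: the next-business-day rule (Section 6 calendar note; Section 6.2). Clock times are assumed: injection at 10:00, contact between 09:00 and 17:00. For a contact d calendar days later, the time from injection runs from 24d − 1 to 24d + 7 hours. Subtracting 10 gives the time since the window closed.

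| Scan day | d (days) | Hours since injection | Hours since window closed |
|---|---|---|---|
| Monday to Thursday | 1 | 23–31 | 13–21 |
| Friday | 3 | 71–79 | 61–69 |
| Friday before a Monday holiday | 4 | 95–103 | 85–93 |

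**3. Size.** Section 3 plans 14 subjects in Cohort 1 out of 25: 14/25 = 56%. This is the share of subjects to whom the gap applies, not the share with a missed event.

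The documents give neither a true event rate p nor a recall probability s, so the following is only an illustration with assumed values. With n = 14:

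- expected missed events = 14 × p × (1 − s)
- P(at least one recorded) = 1 − (1 − p × s)^14

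| Assumed p | Assumed s | Expected missed | P(at least one recorded) |
|---|---|---|---|
| 2% | 100% | 0 | 0.25 |
| 2% | 50% | 0.14 | 0.13 |
| 5% | 100% | 0 | 0.51 |
| 5% | 75% | 0.18 | 0.41 |
| 5% | 50% | 0.35 | 0.30 |
| 10% | 100% | 0 | 0.77 |
| 10% | 50% | 0.70 | 0.51 |

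Across this range fewer than one event is missed on average, at most 0.70. In a cohort of 14, though, losing one event can decide whether any event is seen at all: at p = 5%, that chance falls from 0.51 with full recall to 0.30 with half recall.

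**The case against.** Several points on the other side are sound.

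- **Collection is not only delayed recall.** The Section 9.2 sentence concerns questioning at visits, including the scan day, with examination where appropriate, and staff watch for allergic reaction during the scan. This stands, but it cannot cover events after the subject goes home.
- **The partner is not excluded.** The text is silent, and a partner willing to come to visits may well be present on scan day. This also stands. However, the partner's stated duty concerns visits, so a site could telephone the subject alone and be fully compliant.
- **Impairment is mild and no reactions are expected.** Cohort 1 needs an MMSE of at least 24, and Section 1.3 reports no events in about 3,450 people. Both limit the likely size. Neither removes the reliance on memory in a cohort defined by memory loss.

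A reader might go further than the documents allow in three ways.

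- **That the protocol already rejects telephone contact with an MCI subject alone.** Section 4.5 does say that "a verbal consent discussion by phone will only occur if both the patient and the study partner are available for the discussion". That rule concerns consent and makes no judgement on symptom reports. The lumbar puncture provision in Section 6.1 is likewise permissive.
- **That events will be under-recorded.** Without a rate or a recall figure, only that they may be.
- **That tolerability will not be comparable across cohorts.** The objectives (Section 2), analysis variables (Section 7.2) and statistical methods (Section 8.2) contain no such comparison.

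**Conclusion.** The gap is real and modest. For 14 of 25 planned subjects, the only named informant is a person with amnestic impairment. About 9 of the 10 hours lie outside the scan, and the single later contact comes 1, 3 or 4 calendar days after it. Transient events at home may be missed. The number cannot be stated from the documents; the illustration gives at most 0.70 missed events among 14 and rests wholly on assumed rates (2% to 10%) and recall (50% to 100%). No planned efficacy or between-cohort analysis is affected. The change is worth making because it is cheap and improves safety ascertainment.

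A firmer recording problem lies beside it. Section 6.2 says that grade 3 or higher events are recorded for the 10 hours, while Section 9.2 says that all events in the same period are. Under the Section 6.2 wording, a mild event might go unrecorded even if perfectly remembered. Changing the informant does not settle that conflict.

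**What to change.** In the follow-up note to the study calendar and in Section 6.2, state that for Cohort 1 the study partner or legal representative is asked about adverse events as well as the subject, and that the contact is not delayed if that person cannot be reached. Add the same for visit questioning in Section 9.2. Record on the CRF who gave the information and when the contact took place.

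The cost is a sentence in each of these places and two CRF fields. No visit is added, and eligibility and analysis do not change. The drawback is having to coordinate the contact with two people.

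Separately, reconcile Sections 6.2 and 9.2 on which grades of event are recorded.
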